6.2 Exclusion Criteria

Subjects are excluded from the study if any of the following criteria apply.

1. History of anaphylaxis, hypersensitivity, or any serious reaction to the echinocandin class of antifungals and/or excipients of this formulation, including, but not limited to, hereditary sugar disorders (e.g., fructose intolerance, sucrase-isomaltase deficiency), or echinocandin-induced exfoliative skin disorders (e.g., Stevens-Johnson syndrome or toxic epidermal necrolysis)

2. Subject has a concurrent medical condition that in the opinion of the Investigator and/or medical monitor precludes enrolment into the study
3. Evidence of impaired hepatic or renal functions, as defined by aspartate aminotransferase (AST) or alanine aminotransferase (ALT) >3 times the upper limit of normal (ULN), conjugated bilirubin >24 µmol/L (1.4 mg/dL), serum creatinine >177 µmol/L (2 mg/dL), or receiving renal replacement therapy
4. The Investigator anticipates the subject becoming anaemic and not tolerating blood draws during the study period
5. Subjects have intestinal hypoxia, ischaemia, necrosis, or necrotising enterocolitis
6. Neonates with hyperbilirubinaemia and requiring phototherapy
7. History of severe ataxia, persistent tremors (e.g., due to persistent hypoglycaemia, persistent hypocalcaemia, encephalopathy, etc.), intracranial haemorrhage, or neuropathy, or a diagnosis of epilepsy, multiple sclerosis, or a movement disorder (including, but not limited to, cerebral palsy and muscular dystrophy), any of which is of Grade 2 or higher, based on the Division of Acquired Immunodeficiency Syndrome (DAIDS) criteria, Version 2.1
8. Planned or ongoing therapy at Screening or during the course of the study with a known severe neurotoxic medication (see [Appendix 4](#)) or CNS irradiation, or with a known moderate neurotoxic medication in a subject with ataxia, persistent tremors, intracranial haemorrhage, motor neuropathy, or sensory neuropathy, any of which is of Grade 1 or higher, based on the DAIDS criteria, Version 2.1 (see [Appendix 3](#))
 - a. Coadministration of vincristine (maximum: 2 mg/dose) with a dosing interval of every 21 days or less frequent is permitted in subjects without a history of ataxia, persistent tremors, intracranial haemorrhage, motor neuropathy, or sensory neuropathy **AND** not receiving concomitant azole therapy during the course of the study (from signing the informed consent to the follow-up visit on Day 30 ± 5).
9. Subject status is unstable (e.g., with sepsis or disseminated intravascular coagulation) and unlikely to complete required study procedures
10. Subject is currently receiving an echinocandin (or has received an echinocandin within 5 days before administration of rezafungin)
11. Previous participation in this study or any previous rezafungin study
12. Participation in another interventional treatment trial with an unapproved investigational agent or presence of an unapproved investigational device at the time of informed consent or within 28 days preceding study entry (informed consent)

Note: Participation in investigational trials involving approved chemotherapeutic or immunological regimens, investigational radiotherapy trials, and observational trials are allowed.
13. Pregnant or lactating females
14. The Investigator is of the opinion the subject should not participate in the study
15. Subjects/LARs dependent on the Sponsor, Investigator or study site

16. Unable to give his/her own informed consent if a subject reaches the age of consent during the study
17. Committed to an institution in accordance with an order issued either by the judicial or the administrative authorities
18. Tested positive for severe acute respiratory syndrome coronavirus 2 (SARS-CoV-2) by a nucleic acid amplification test or antigen test within 7 days prior to dosing of rezafungin (note, SARS-CoV-2 testing is not a protocol requirement and should be performed according to the institutional policy and clinical need)

6.3 Lifestyle Considerations

It is expected that all the subjects will receive rezafungin IV infusion in a hospital setting; subjects may be permitted to complete PK assessments on an outpatient basis if deemed appropriate by the Investigator.

6.4 Screen Failures

After signing the informed consent, subjects who drop out or withdraw from the study for any reason without completing all Screening evaluations, or subjects who do not meet the eligibility criteria will be considered screen failures.

Subjects who do not meet the criteria for participation may be rescreened. Subjects are only allowed to be rescreened once; the entire screening process must be repeated. Rescreened subjects will be assigned a new subject number for every screening/rescreening event.

7 STUDY TREATMENT

The details of the study treatment (IV rezafungin) are provided in [Table 3](#).

7.1 Study Treatment Administered

This is an open-label study and all subjects will receive a single IV infusion of rezafungin over 2 hours (\pm 5 minutes).

Part 1 (Group 1 – 12 to <18 years of age)

The IP formulation used for Group 1 will be same as the one used in the adult clinical trials. Dose for Group 1 will be 3 mg/kg (not to exceed a total dose of 200 mg).

Part 2 (Group 2 – 6 to <12 years and Group 3 – 2 to <6 years of age) and Part 3 (Group 4 – from birth to <2 years of age)

In parallel to this clinical study, a formulation development programme is being undertaken to identify a lower strength paediatric specific formulation with an appropriate PS80 level for use in subjects <12 years of age. When an adequate paediatric formulation is identified, after the completion of Group 1, the study will be paused and a substantial amendment will be submitted to enable the paediatric formulation to be used in the subjects in Groups 2, 3, and 4.

The planned dose for Group 2 and Group 3 is 4 mg/kg (not to exceed a total dose of 200 mg) and the planned dose for Group 4 is 5 mg/kg; however, the doses will be confirmed after assessment of the interim PK and safety data. The doses may be adjusted as appropriate.

Table 3 Study Treatment Administered

Study Treatment	Test Product
Study Treatment Name	Rezafungin acetate (MR907)
Treatment Description	
Part 1: Rezafungin is a sterile product of lyophilised powder for reconstitution with sterile water for injection prior to dilution into infusion bags containing normal saline, half-normal saline, or 5% dextrose. Each single-dose vial contains rezafungin acetate (200 mg of active rezafungin) and excipients, including polysorbate 80 (450 mg), mannitol (500 mg), and histidine (47 mg). The formulation may contain hydrochloric acid and/or sodium hydroxide as needed for pH adjustment.
 
After reconstitution of the lyophilised powder with water for injection, the reconstituted solution should be immediately diluted into infusion bags containing normal saline, half-normal saline or 5% dextrose.
 
Part 2 and Part 3: Formulation information will be included when available.

Formulation	Powder for concentration for solution for infusion (for Part 1). Formulation for Part 2 and Part 3 will be included when available.
Unit Dose Strength	200 mg/vial (for Part 1)
Dose(s)	
Age-appropriate doses (as a single dose)
 
 • 3 mg/kg (not to exceed a total dose of 200 mg) for 12 to <18 years (Group 1) • 4 mg/kg (not to exceed a total dose of 200 mg) for 2 to <12 years (Group 2 and Group 3) • 5 mg/kg for subjects from birth to <2 years (Group 4)
Route of Administration	Intravenous infusion over 2 hours (\pm 5 minutes)
Packaging and Labelling	
Labelling and packaging of study medication will be as per applicable regulatory requirements.
 
Study medication must be stored in a secure, limited access area, and may be dispensed only by specifically authorised personnel.
 
Refer to the Pharmacy Manual for further details on packaging, labelling, and storage.

Manufacturer	Patheon, Monza, Italy

7.2 Administration

Subjects will receive a single IV dose of rezafungin as a 2-hour (\pm 5 minutes) IV infusion.

For Group 1, rezafungin will be reconstituted with water for injection. The reconstituted solution should be immediately diluted into infusion bags containing normal saline, half-normal saline or 5% dextrose. Age-appropriate volumes (based on body weight) will be used to dilute reconstituted rezafungin with final concentrations between 0.8 and 1.6 mg/mL. Infusion rates will differ based on the volume of each dose in each subject, and will be between 0.9375 and 1.875 mL/kg/hour. The PS80 infusion rate will be 0.0563 mg/kg/min. Please refer to the

Pharmacy Manual for the detailed directions for preparation and administration of rezafungin intravenous solution.

Once the paediatric formulation for Groups 2, 3, and 4 is available, the method of administration will be determined and included in the protocol via a substantial amendment.

7.3 Preparation/Handling/Storage/Accountability

The study treatment will be supplied to the Investigator or designee by the Sponsor, either directly or via a local warehouse contracted by the Sponsor.

The Investigator or designee must confirm appropriate temperature conditions have been maintained during transit for all study treatment received, and any discrepancies are reported and resolved before use of the study treatment.

Only subjects enrolled in the study may receive study treatment, and only authorised site staff may supply or administer study treatment. All study treatment must be stored in the packaging to protect from light, in a secure, environmentally controlled, and monitored (manual or automated) area in accordance with the labelled storage conditions with access limited to the Investigator and authorised site staff.

The Investigator, institution, or the head of the medical institution (where applicable) is responsible for study treatment accountability, reconciliation, and record maintenance (i.e., receipt, reconciliation, and final disposition records).

Unused study treatments including empty containers, are to be returned to the Sponsor or Sponsor-designated warehouse at the conclusion of the study, unless provision is made by the Sponsor for destruction of supplies and containers at the investigational site.

Further guidance and information for the final disposition of unused study treatments are provided in the Pharmacy Manual.

7.4 Measures to Minimise Bias: Randomisation and Blinding

Not applicable as this is an open-label, single-arm study.

7.5 Treatment Compliance

The IP (rezafungin) will be administered at the site (hospital). Subjects will receive the infusion from the Investigator or designee, under medical supervision. The date and time of the infusion and dose administered will be recorded in the source documents. The dose of IP and subject identification will be confirmed at the time of dosing by a member of the study site staff other than the person administering the study treatment.

Compliance will be documented in the source documents and relevant medical and pharmacy records. Deviation(s) from the prescribed dose regimen (e.g., dose, infusion volume, and infusion duration) should be recorded.

7.6 Dose Modification

If any mild local infusion-related reaction occurs, the Investigator may temporarily slow or discontinue the infusion, or re-site the infusion. If any systemic or moderate/severe local infusion-related reaction occurs, the Investigator may stop the infusion and inform the Sponsor/medical monitor.

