Analysis of the safety data obtained in ReSTORE indicates that rates of TEAEs and SAEs were comparable between the rezafungin and caspofungin arms. There were no apparent imbalances between the treatment groups in System Organ Classes (SOCs) of AEs. Related SAEs were similar in number between the two groups. There were no laboratory abnormalities that were commonly associated with either study drug, though there were some imbalances in

the 2-grade increases in toxicity for liver function tests that favours rezafungin. Furthermore, there were no apparent differences noted between vital sign and ECG data among the treatment groups.

Two specific types of AEs were found to be associated with rezafungin in clinical trials: infusion-related reactions and phototoxicity. In ReSTORE, there were 2 cases of infusion intolerance associated with rezafungin dosing and one in the caspofungin arm. While an AE of sunburn was observed in one subject in the Phase 2 STRIVE study following prolonged exposure to the sun, no phototoxicity occurred in the ReSTORE study.¹

Due to the findings of tremors in monkeys exposed to prolonged, high doses (9.2X the exposure to the proposed commercial dose in adults), close attention was paid to any neurologic AEs (i.e., ataxia, neuropathy, and tremor). These neurologic AEs were balanced between the rezafungin and caspofungin study groups, with 2 subjects having tremors in the rezafungin group (0 in the caspofungin group) and 2 subjects having neuropathy in the caspofungin group (0 in the rezafungin group). These 2 cases of tremors were mild in severity and reversible.

More detailed information about the known and expected benefits and risks and reasonably expected AEs of rezafungin (based on the adult clinical trials) can be found in the IB.

Summary of Benefit and Risk Evaluation

As this is a single-dose study, there is no direct clinical benefit expected for the subjects who will participate in this study. The information obtained from this study will be used for the further clinical development of rezafungin in the paediatric population.

The risk of AEs is minimised by careful selection of doses and participants for the study, the relatively short duration (single dose) of IP exposure, lowered infusion rate, and the extent of safety monitoring incorporated into the study.

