8 DISCONTINUATION OF STUDY TREATMENT AND SUBJECT DISCONTINUATION/ WITHDRAWAL

8.1 Discontinuation of Study Treatment

This is a single-dose study. All subjects enrolled will receive a single infusion of IP (rezafungin).

Stopping Rules

Stopping Criteria for an Individual Subject

- In case of any systemic reaction (i.e., cytokine release syndrome, including nausea, headache, tachycardia, hypotension, rash, and/or shortness of breath) or local infusion-related reaction (i.e., injection site pain or tenderness, erythema or redness, induration or swelling, or pruritis) with a severity of Grade 2 or higher (according to the DAIDS criteria, Version 2.1), the infusion will be immediately stopped and not restarted, and treatment provided as appropriate. The date and time of discontinuation must be recorded in the eCRF. The Sponsor/medical monitor must be informed immediately (no later than 24 hours of Principal Investigator's knowledge of the event). Where feasible, the PK assessment will continue if the subject is well enough and willing to continue.
Note: in case of Grade 1 local reactions, the investigator may slow down the infusion or temporarily discontinue the infusion (see Section 7.6).
- A subject becomes pregnant.

Criteria for Pausing or Stopping the Study

The study would be paused in cases where:

- One subject experiences a serious unexpected adverse event that is considered at least possibly related to rezafungin. The event will be investigated and the causality established before dosing the next available subject.

The study would be stopped in cases where any of the following occurs:

- A study drug-related significant adverse reaction (i.e., a serious AE considered at least possibly related to the IP administration) leading to treatment discontinuation in 2 subjects
- Two or more subjects have experienced a Grade ≥ 4 AE considered to be related to rezafungin
- The Investigator and the Sponsor both agree that the tolerability profile is unacceptable, based on the frequency and intensity of observed AEs (including serious and related AEs)
- At the request of the DSMB, based on a safety concern during the review of the safety and tolerability data

- Additional data from other clinical trials or toxicological studies become available that negatively influence the risk/benefit assessment
- At a specific site/in a specific region: if the local regulatory authority or Independent Ethics Committee (IEC) withdraws approval of the study

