Investigators will grade all AEs by severity using DAIDS (Version 2.1). If an AE is not listed in the DAIDS criteria, a corresponding grading is to be performed by the Investigator based on his/her best medical judgement as follows:

- Mild (Grade 1): Mild symptoms causing no or minimal interference with usual social & functional activities with intervention not indicated
- Moderate (Grade 2): Moderate symptoms causing greater than minimal interference with usual social & functional activities with intervention indicated
- Severe (Grade 3): Severe symptoms causing inability to perform usual social & functional activities with intervention or hospitalization indicated
- Life-threatening (Grade 4): Potentially life-threatening symptoms causing inability to perform basic self-care functions with intervention indicated to prevent permanent impairment, persistent disability, or death
- Death (Grade 5): all deaths related to an AE

Assessment of Causality

- The Investigator is obligated to assess the relationship between study treatment and each occurrence of each AE/SAE. The Investigator will use clinical judgement to determine the relationship.
- A reasonable possibility of a relationship conveys that there are facts, evidence, and/or arguments to suggest a causal relationship, rather than a relationship cannot be ruled out.
- For each AE/SAE, the Investigator must document in the medical notes that he/she has reviewed the AE/SAE and has provided an assessment of causality.
- There may be situations in which an SAE has occurred and the Investigator has minimal information to include in the initial report to the Sponsor. However, it is very important that the Investigator always make an assessment of causality for every event before the initial transmission of the SAE data to the Sponsor.
- The Investigator may change his/her opinion of causality in light of follow-up information and send an SAE follow-up report with the updated causality assessment.
- The causality assessment is one of the criteria used when determining regulatory reporting requirements.

Causality:

Related

- Related: The AE follows a reasonable temporal sequence to IP administration, and it is a known reaction to the drug under study or a related chemical group or is predicted by known pharmacology

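### Section 7.6 leaves it to the Investigator whether to stop the infusion for reactions that Section 8.1 says must end it

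*Combined protocol and SAP*

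**What the plan says.** Section 7.6 has two sentences on infusion reactions. For mild local reactions, "the Investigator may temporarily slow or discontinue the infusion, or re-site the infusion". For the rest: "If any systemic or moderate/severe local infusion-related reaction occurs, the Investigator may stop the infusion and inform the Sponsor/medical monitor".

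Section 8.1, under its stopping criteria for an individual subject, deals with systemic and local infusion reactions together and says that "with a severity of Grade 2 or higher (according to the DAIDS criteria, Version 2.1), the infusion will be immediately stopped and not restarted". It adds: "The Sponsor/medical monitor must be informed immediately (no later than 24 hours" of the Principal Investigator learning of the event). A note then says that "in case of Grade 1 local reactions, the investigator may slow down the infusion or temporarily discontinue the infusion (see Section 7.6").

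The link between severity words and grades is in Appendix 3 (Assessment of Intensity), "Moderate (Grade 2): Moderate symptoms causing greater than minimal interference" and "Severe (Grade 3): Severe symptoms causing inability to perform", and again in Section 10.4.5.

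**The concern.** Both sections are current text and give different instructions for the same bedside event. One uses a permissive verb. The other is compulsory and bars a restart. Section 7.6 is a natural place to look when a reaction starts during a two-hour infusion, and a reader who stops there finds only a discretion. The single cross-reference runs from 8.1 to 7.6 and concerns Grade 1 local reactions, where the sections agree. A reader who follows it arrives next to the discretionary sentence.

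At stake is whether the subject-level stopping rule is applied uniformly. Section 5.2 describes this as the first study of the drug in children. Section 3.3 expects no direct clinical benefit for those taking part and names infusion-related reactions as one of two types of adverse event associated with rezafungin in clinical trials.

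**Working it through.** No arithmetic applies. The check sets the two sections side by side, grade by grade.

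**Inputs**
- Section 7.6, first sentence: mild local reactions; slow, interrupt or re-site at discretion.
- Section 7.6, second sentence: all systemic reactions, plus moderate or severe local ones; stopping at discretion.
- Section 8.1: systemic or local reactions, threshold DAIDS Grade 2; stop at once, no restart.
- Mapping: mild = Grade 1, moderate = Grade 2, severe = Grade 3, life-threatening = Grade 4. Appendix 3 introduces this wording for events that DAIDS does not list. Section 10.4.5 gives the same mapping without that limit, so the overlap does not depend on the Appendix 3 qualifier.

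**Comparison**

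| Reaction | Section 7.6 | Section 8.1 | Consistent? |
|---|---|---|---|
| Local, Grade 1 | May slow, interrupt or re-site | May slow or interrupt; refers to 7.6 | Yes |
| Local, Grade 2 or 3 | May stop | Must stop, no restart | No |
| Local, Grade 4 | Not named by its severity words | Must stop, no restart | 7.6 is silent |
| Systemic, Grade 1 | May stop | No compulsory stop if the threshold covers systemic reactions | Depends on the reading of 8.1 |
| Systemic, Grade 2 or higher | May stop | Must stop, no restart | No |

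**Grade 1 systemic reactions.** The natural reading of 8.1 attaches the Grade 2 threshold to systemic and local reactions alike. In that case 7.6 alone governs Grade 1 systemic reactions, and its permissive verb is right for them. The 8.1 sentence can also be read as attaching the threshold to local reactions only, so that any systemic reaction ends the infusion. On that reading the conflict with 7.6 would extend to Grade 1 systemic reactions. Either way, it stands from Grade 2 upwards.

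**Which section reflects the intent.** The heading and graded threshold of 8.1 mark it as the operative rule. As context only, the amendment history (Appendix 9, Amendment 1) records that the individual stopping criteria were moved from Investigator judgement to DAIDS severity. The conflict does not rest on that entry, because both sentences are in force now.

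**Frequency.** Section 3.3 says of the adult Phase 3 trial that "there were 2 cases of infusion intolerance associated with rezafungin dosing and one in the caspofungin arm". Grades are not given, so no paediatric rate of Grade 2 or higher reactions can be derived, and none is claimed.

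**The case against.** The strongest reply is that permissive and compulsory wording can both be obeyed. Section 7.6 tells nobody to continue. Section 8.1 is the more specific rule and sits under a stopping-rules heading, and an Investigator who continues at Grade 2 breaches it whatever 7.6 says. The permissive verb is also correct for part of the class that 7.6 covers, namely Grade 1 systemic reactions on the natural reading of 8.1. Dosing takes place in hospital under medical supervision (Section 7.5), with vital signs and ECG monitored throughout the infusion (Section 5.1.4).

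All of that stands, and it limits the size of the point. It does not remove it: 7.6 neither defers to 8.1 nor separates Grade 1 from higher grades, and supervision and monitoring do not restate the compulsory stop.

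Three stronger readings are tempting, and the documents do not support them:

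- A reader might infer that 7.6 allows a stopped infusion to be restarted after a Grade 2 reaction. It does not. Its only mention of temporary interruption is for mild local reactions, and 8.1 bars a restart from Grade 2 upwards.
- A reader might infer that telling the Sponsor has become optional, because the permissive verb in 7.6 also governs that clause. It has not. Section 8.1 makes notification compulsory within 24 hours. Section 9.2.6 and Appendix 3 separately require infusion-related reactions to be reported within 24 hours as events of special interest, even if non-serious and with no grade threshold.
- A reader might infer that Section 9 reopens the decision, since it asks for safety concerns to be discussed with the Sponsor to settle whether treatment continues. That is a general statement about any safety concern. It does not address infusion reactions from Grade 2 upwards and does not displace 8.1.

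**Conclusion.** The point holds as an internal inconsistency. For local reactions of Grade 2 or 3, and for systemic reactions of Grade 2 or higher, 7.6 makes optional what 8.1 makes compulsory. The severity is modest: one sentence of 7.6 is affected, 8.1 is clear at these grades, and an Investigator who follows 8.1 complies with both. It is still worth correcting, because the rule protects individual children and the remedy is a wording change.

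The conclusion rests on the protocol's own mapping of moderate to Grade 2 and severe to Grade 3. It needs no assumption about how often such reactions occur, and it does not depend on how 8.1 is read for Grade 1 systemic reactions. It should not be taken as evidence that any infusion has been or will be continued wrongly.

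**What to change.** Keep the first sentence of 7.6 for mild (Grade 1) local reactions. Replace the second sentence with two, to this effect:

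- *For any systemic or local infusion-related reaction of DAIDS Grade 2 or higher, the infusion must be stopped at once and must not be resumed, and the Sponsor/medical monitor must be informed, as Section 8.1 requires.*
- *For a Grade 1 systemic reaction, the Investigator may stop the infusion and will inform the Sponsor/medical monitor.*

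The second of these is needed: without it, the replacement would delete the only text in 7.6 on Grade 1 systemic reactions. Using a grade threshold also brings in Grade 4 local reactions, which the present severity words do not name.

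In 8.1, confirm that the Grade 2 threshold applies to systemic as well as local reactions. If the sponsor instead intends any systemic reaction to end the infusion, the second new sentence in 7.6 must change to match.

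The cost is two sentences in 7.6 and a clarifying phrase in 8.1, plus the ethics committee approval that Appendix 1 requires for amendments. Design, sample size, data collection and analysis are untouched. The substantial amendment already planned after Part 1 (Section 5.1) could carry the edit, but waiting for it would leave any Group 1 subject dosed before then under the present wording, so an earlier amendment is preferable if Group 1 dosing is still open.
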